6.6.6. Context and rationale for follow up

Only intention-to-treat (ITT) analyses will be conducted. Although cross-over from the exposure to the comparator can be expected which biases the exposure treatment effect more towards the null, this also applies to the RCT. According to Slamon et al., although cross-over was not permitted during the study, a total of 399 (89.9%) patients in the palbociclib plus letrozole arm and 217 (97.7%) in the placebo plus letrozole arm discontinued treatment. 47 (11.8%) and 58 (26.7%) patients received a CDK4/6 inhibitor(s) poststudy, respectively; of these, the majority received palbociclib (74.5% in the palbociclib plus letrozole arm and 89.7% in the placebo plus letrozole arm, which would constitute a crossover).⁶

An as-treated analysis is not considered since in the context of oncology, reasons for discontinuation usually are due to toxicity, death or progression/non-response to the current treatment, all of which are highly correlated with the outcome under study which would hence lead to bias due to informative censoring.

6.6.7. Context and rationale for covariates

We identified a series of covariates that are strong prognostic factors for the outcome and auxiliary covariates which may be useful to impute missing data. Such covariates comprise demographics, covariates indicating disease-severity, cancer-specific covariates as well as pathological and genetic factors. In addition, selected labs and vitals are considered since they were shown to carry a high amount of prognostic information as described in Becker, Weberpals, et al.¹¹ For these variables, additional plausibility checks and transformations are carried out. In detail, labs and vitals are individually checked if they cross a certain biologically implausible threshold (e.g., a heart rate of 0) in which cases the values are set missing and imputed in a next step. These thresholds were compiled by experienced practicing physicians and medical oncologists and are listed in appendix **Table 8** and **Table 9**.

Note that not all covariates are available across all databases used for this trial emulation. In the analytical stage, the most comprehensive model will be fit for each database individually.

Table 5. Operational definitions of key covariates used for trial emulation.

Characteristic	Harmonized analysis variable name	R function to derive covariate (see pdf in appendix)	Details ¹	Variable encoding	Assessment window
Age at index date	dem_age_index	edbx_get_demographics()	Age measured at index date	Binary (<60, 65+); modelled continuously in ROPRO ¹⁰	[0;0]
Year of index date	c_year_index	De novo derived from dt_index	Calendar year in which patient initiated study treatment	Nominal (<2020, 2020+)	[0;0]
Family history	dem_family_history	edbx_get_demographics()	Family history of cancer. Not available in EDB1.	Logical (TRUE, FALSE)	[0;0] (no specific date is associated)
Race	dem_race	edbx_get_demographics()	Race categorized as in the original RCT	Binary (Asian vs non-Asian)	[0;0]
Ethnicity	dem_ethnicity	edbx_get_demographics()	Ethnicity	Hispanic, Non-Hispanic	[0;0]
Region	dem_region	edbx_get_demographics()	US region patient receives care in; if given on a state level, region is manually mapped (see Table 10)	Nominal (Northeast, South, West, Midwest)	[0;0]
Practice type	dem_practice	edbx_get_demographics()	Setting patient is receiving care at. Not available in EDB3 and EDB4.	Nominal (academic, community, academic & community)	[-inf;0]
Socio-economic status	dem_ses	edbx_get_demographics()	Socioeconomic status (SES) index based on residence area of patient. Not available in EDB3 and EDB4.	Nominal (from '1 - Lowest SES' through '5 - Highest SES')	[-inf;0]
Smoking	c_smoking_history	edbx_get_demographics()	History of current or former (= TRUE) or never (= FALSE) smoking on or anytime before index date; if there are multiple records per patient, any evidence of former/current smoking is prioritized. IN EDB1, "smoking history" is not available for breast cancer.	Binary logical (TRUE, FALSE)	[-inf;0]
ECOG	c_ecog	edbx_get_ecog()	ECOG performance status measured closest to index date within assessment window. In	Nominal (0, 1, 2, 3, 4); modelled as ordinal numeric in ROPRO ¹⁰ ; due to I/E	[-90;0]

Characteristic	Harmonized analysis variable name	R function to derive covariate (see pdf in appendix)	Details ¹	Variable encoding	Assessment window
			case of ties, the lower ECOG value is selected	criteria ECOG is modelled as a binary (0, 1) covariate	
Stage	c_stage_initial_dx	edbx_get_diagnosis_solid()	AJCC summary group stage at initial diagnosis	Ordinal numeric (from 0 to IV with sub-categories, e.g., IA1) ¹⁰	[-inf;0] at initial diagnosis of primary cancer
De novo metastatic status	c_de_novo_mets_dx	edbx_get_diagnosis_solid()	Evidence of presence of one or multiple metastases at/before initial diagnosis	Binary logical (TRUE, FALSE)	[-inf;0] at initial diagnosis of primary cancer
Number of metastatic sites	c_number_met_sites	edbx_get_diagnosis_solid()/edbx_get_number_met_sites_solid()	Number of metastatic sites for a given patient before/on index date	Integer	[-inf;X]; Proprietary business-rule-based covariate assessment window
Time between initial diagnosis to index date	c_time_dx_to_index	edbx_get_diagnosis_solid()	Time in days between initial diagnosis to index date. Quartiles will be used because there may be “negative” times intervals due to date imprecision of the lines of therapy.	Categorical (quartiles)	[-initial dx;0]
Time between earliest evidence of a metastatic and index date	c_time_met_dx_to_index_quartiles	edbx_get_diagnosis_solid()	Time in days between earliest evidence of a metastatic diagnosis and index date. Quartiles will be used because there may be “negative” times intervals due to date imprecision of the lines of therapy.	Categorical (quartiles)	[met dx;0]
Histology (adenocarcinoma)	c_histology_match	edbx_get_histology()	Evidence of adenocarcinoma histology (non-squamous cell for EDB1)	Binary logical (TRUE, FALSE)	[-inf;0]
Albumin	c_albumin_g_l_cont	edbx_get_labs()	Closest albumin measurement (in serum/plasma) relative to index date in g/L. In case of ties, the lower is selected	Continuous	[-90;0]
Alkaline phosphatase (ALP) ²	c_alp_u_l_cont	edbx_get_labs()	Closest alkaline phosphatase measurement (in serum/plasma) relative to index date in U/L. In case of ties, the lower is selected	Continuous	[-90;0]
Alanine aminotransferase (ALT) ²	c_alt_u_l_cont	edbx_get_labs()	Closest alanine transaminase measurement (in serum/plasma) relative to index date in U/L. In case of ties, the lower is selected	Continuous	[-90;0]

Characteristic	Harmonized analysis variable name	R function to derive covariate (see pdf in appendix)	Details ¹	Variable encoding	Assessment window
Aspartate aminotransferase (AST)	c_ast_u_l_cont	edbx_get_labs()	Closest aspartate aminotransferase measurement (in serum/plasma) relative to index date in U/L. In case of ties, the lower is selected. Used to compute AST-ALT ratio	Continuous	[-90;0]
AST/ALT ratio	c_ast_alt_ratio_cont	edbx_get_labs()	AST/ALT ratio calculated from c_ast_u_l_cont/c_alt_u_l_cont	Continuous	[-90;0]
Bilirubin ²	c_bilirubin_mg_dl_cont	edbx_get_labs()	Closest bilirubin measurement (in serum/plasma) relative to index date in mg/dL. In case of ties, the lower is selected	Continuous	[-90;0]
Calcium ²	c_calcium_mg_dl_cont	edbx_get_labs()	Closest calcium measurement (in serum/plasma) relative to index date in mg/dL. In case of ties, the lower is selected	Continuous	[-90;0]
Chloride	c_chloride_mmol_l_cont	edbx_get_labs()	Closest chloride measurement (in serum/plasma) relative to index date in mmol/L. In case of ties, the lower is selected	Continuous	[-90;0]
Eosinophils/100 leukocytes ²	c_eosinophils_leukocytes_ratio_cont	edbx_get_labs()	Eosinophils/100 leukocytes in blood. In case of ties, the lower	Continuous	[-90;0]
Glucose ²	c_glucose_mg_dl_cont	edbx_get_labs()	Closest glucose measurement (in serum/plasma) relative to index date in mmol/L. In case of ties, the lower is selected	Continuous	[-90;0]
Granulocyte/leukocyte ratio ²	c_granulocytes_leukocytes_ratio	edbx_get_labs()	Closest granulocyte/leukocyte ratio measurement (in blood) relative to index date. In case of ties, the lower is selected. Used to compute granulocyte/lymphocyte ratio	Continuous	[-90;0]
Hemoglobin	c_hemoglobin_g_dl_cont	edbx_get_labs()	Closest hemoglobin measurement (in blood) relative to index date in g/L. In case of ties, the lower is selected	Continuous	[-90;0]
Lactate dehydrogenase (LDH) ³	c_ldh_u_l_cont	edbx_get_labs()	Closest LDH measurement (in serum or plasma) relative to index date in U/L. In case of ties, the lower is selected	Continuous	[-90;0]

Characteristic	Harmonized analysis variable name	R function to derive covariate (see pdf in appendix)	Details ¹	Variable encoding	Assessment window
Lymphocytes	c_lymphocyte_10_9_l_cont	edbx_get_labs()	Closest lymphocytes measurement (in blood) relative to index date in 10 ⁹ /L. In case of ties, the lower is selected. Used to compute neutrophil/lymphocyte ratio	Continuous	[-90;0]
Lymphocyte/leukocyte ratio ²	c_lymphocyte_leukocyte_ratio_cont	edbx_get_labs()	Closest lymphocyte/leukocyte ratio measurement (in blood) relative to index date. In case of ties, the lower is selected. Used to compute neutrophil/lymphocyte ratio	Continuous	[-90;0]
Monocytes ²	c_monocytes_10_9_l_cont	edbx_get_labs()	Closest monocytes measurement (in blood) relative to index date in 10 ⁹ /L. In case of ties, the lower is selected.	Continuous	[-90;0]
Neutrophils	c_neutrophil_10_9_l_cont	edbx_get_labs()	Closest neutrophils measurement (in blood) relative to index date in 10 ⁹ /L. In case of ties, the lower is selected. Used to compute neutrophil/lymphocyte (NLR) ratio	Continuous	[-90;0]
Neutrophil/lymphocyte ratio ²	c_neutrophil_lymphocyte_ratio_cont	edbx_get_labs()	Neutrophil/lymphocyte (NLR) ratio calculated from c_neutrophil_10_9_l_cont/ c_lymphocyte_10_9_l_cont	Continuous	[-90;0]
Platelets	c_platelets_10_9_l_cont	edbx_get_labs()	Closest platelets measurement (in blood) relative to index date in 10 ⁹ /L. In case of ties, the lower is selected	Continuous	[-90;0]
Protein	c_protein_g_l_cont	edbx_get_labs()	Closest protein measurement (in serum/plasma) relative to index date in g/L. In case of ties, the lower is selected	Continuous	[-90;0]
Urea nitrogen ²	c_urea_nitrogen_mg_dl_cont	edbx_get_labs()	Closest urea nitrogen measurement (in serum/plasma) relative to index date in mg/L. In case of ties, the lower is selected	Continuous	[-90;0]
Systolic blood pressure ²	c_sbp_cont	edbx_get_vitals()	Closest systolic blood pressure (in mmHg) measurement. In case of ties, the lower is selected	Continuous	[-90;0]

Characteristic	Harmonized analysis variable name	R function to derive covariate (see pdf in appendix)	Details ¹	Variable encoding	Assessment window
Body mass index (BMI) ²	c_bmi_cont	edbx_get_vitals()	Closest BMI measurement (in kg/m ²) relative to index date. In case of ties, the lower is selected.	Continuous	[-90;0]
Heart rate ²	c_hr_cont	edbx_get_vitals()	Closest heart rate measurement (in bpm) relative to index date. In case of ties, the lower is selected	Continuous	[-90;0]
Oxygen saturation	c_oxygen_cont	edbx_get_vitals()	Closest heart rate measurement (in bpm) relative to index date. In case of ties, the lower is selected	Continuous	[-90;0]

¹ x stands for the pseudonymized number of the respective database, i.e., EDB1, EDB3 or EDB4

² For calculation of ROPRO prognostic score¹¹, this variable is log transformed.

[figure not shown]
³ For calculation of ROPRO prognostic score¹¹, this variable is log-log transformed.

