The purpose of this protocol is to describe the emulation of the **PALOMA-2** trial. PALOMA-2 was a Phase III, double-blind, randomized study assessing the efficacy and safety of **palbociclib (125 mg orally, once daily for 21 days of a 28-day cycle) in combination with letrozole (2.5 mg orally, once daily, continuously) versus letrozole alone** in postmenopausal women with **estrogen receptor-positive (ER+), human epidermal growth factor receptor 2-negative (HER2–) advanced breast cancer** who had not received prior systemic treatment for their advanced disease.

The primary trial endpoint was **progression-free survival (PFS)** with a hazard ratio (HR) of **0.58** (95% CI, 0.46 to 0.72), based on a **median PFS of 24.8 months** (95% CI, 22.1 to not estimable) in the palbociclib-plus-letrozole group compared with **14.5 months** (95% CI, 12.9 to 17.1) in the letrozole-alone group. The FDA granted palbociclib accelerated approval in [February 2015](#), in combination with letrozole for the treatment of ER-positive, HER2-negative advanced breast cancer as initial endocrine based therapy in postmenopausal women.

Overall survival (OS) was a secondary trial endpoint with a hazard ratio of **0.96** (95% CI, 0.78 to 1.18; one-sided $p = 0.34$) based on a median OS of 53.9 months in the palbociclib-plus-letrozole group and 51.2 months in the letrozole-alone group.

The results of the PFS endpoint were published in the *NEJM* on November 17, 2016 ([PMID 27959613](#)).⁵

The final results of the OS endpoint were published in the *J. Clin. Oncol.* on January 22, 2024 ([PMID 38252901](#)).⁶

5. Research question and objectives

The primary and secondary research question is summarized in Table 1.

A. Primary research question and objective

Table 1. Primary and secondary research questions and objective.

Objective:	To compare the overall survival [OS] in patients who initiated palbociclib plus letrozole versus patients who initiated letrozole alone.
Hypothesis:	Initiation of palbociclib plus letrozole improves OS time as compared to initiation of letrozole alone.

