	
In subgroup analysis, multiple imputation, propensity score matching and balance assessment will be conducted within each subgroup separately. The treatment effect will be estimated for each stratum separately (stratum-specific effects).
 
 1. Age (<65, ≥65) 2. Region (North America, Europe, Asia/Pacific) 3. ECOG (0, 1) 4. Disease-free interval (De-novo metastatic, ≤12 months, >12 months) 
According to Slamon et al,⁶ the subgroup analyses are considered exploratory in nature and performed with no formal statistical testing.

Table 8. Sensitivity analyses – rationale, strengths and limitations.

	What is being varied? How?	Why? (What do you expect to learn?)	Strengths of the sensitivity analysis compared to the primary	Limitations of the sensitivity analysis compared to the primary
Sensitivity #1	Caliper matching on ROPRO prognostic score instead of propensity score	Matching patients on validated prognostic score may be more beneficial to control for (unmeasured) confounding	Matches patients on validated prognostic score that incorporates weights of key prognostic factors	Limited experience on how to optimally use prognostic scores and should be seen as an experimental sensitivity analysis
Sensitivity #2	Average treatment effect in the overlap population (ATO) weighting instead of matching	Weights that resemble the average treatment effect in the overlap population (ATO) create a clinical equipoise population which is comparable to an RCT	ATO weighting usually results in excellent balance and clinical equipoise	Estimates the average treatment effect among the overlap patients which may not be comparable to target population anymore
Sensitivity #3	SMR/ATT weighting instead of matching. Here symmetric trimming (i.e., setting all weights lower/higher than that at a given quantile to the weight at the quantile) of extreme weights may be considered with the quantiles chosen based on weight distribution and resulting balancing performance.	SMR weighting retains all patients and resembles the same estimand as matching	ATT weighting retains all patients	Patients with extreme weights after trimming may bias the analysis

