10.3. Sample size/power calculations

Power estimations are computed based on the average number of observed events across imputed and matched datasets according to the methodology described by Schoenfeld.³⁹ The OS result was null in the trial, therefore, we are not expecting to observe a strong effect in the emulation. Because our 1:1-matched samples in EDB1 (n=1812) (primary analysis) – are larger than the trial sample (n=666), we expect their confidence intervals to be narrower. In contrast, EDB3 (n=610) was slightly smaller than the trial sample; therefore, we would expect its confidence interval to be slightly wider.

Figure 10 Number of events needed to achieve x% power for overall-survival outcome

Assuming alpha = 0.05, 50% exposed and HR = 0.92

Primary analysis:

- Based on a total of 1021 events in the 1:1-matched set in EDB1, we would achieve a power of 0.27 to detect an effect as large or larger than HR = 0.92.
- Based on a total of 331 events in the 1:1-matched set in EDB3, we would achieve a power of 0.11 to detect an effect as large or larger than HR = 0.92. Even pooling data from EDB1 and EDB3, we are not well powered to detect the expected near null effect based on trial results. Our expectation is that the observed effect size in the emulation will be near null, with tighter confidence intervals.

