Exclusion 1	HER2-positive breast cancer	$[-\infty; 0]$	Any HER2+ status prior to or on index date	Any HER2+ status prior to or on index date	Any HER2+ status prior to or on index date	If HER2 is missing and a patient received the exposures of interest, then HER2 is likely to be negative given the alignment with the indication for the exposures of interest	edbx_get_her2()
Exclusion 2	Patients with advanced, symptomatic, visceral spread, that are at risk of life-threatening complications in the short term (including patients with massive uncontrolled effusions [pleural, pericardial, peritoneal], pulmonary lymphangitis, and over 50% liver involvement).	NA	NA	NA	NA	This is a safety criterion for the trial and less relevant to real-world treatment setting, given that patients received treatments of interest	
Exclusion 3	Known active uncontrolled or symptomatic CNS metastases, carcinomatous meningitis, or leptomeningeal disease as indicated by clinical symptoms, cerebral edema, and/or progressive growth. Patients with a history of CNS metastases or cord compression are eligible if they have been definitively treated with local therapy (eg, radiotherapy, stereotactic surgery) and are clinically stable off anticonvulsants and steroids for at least 4 weeks before randomization.	$[-\infty; 0]$	Record of CNS metastases prior to or on index date	Record of CNS metastases prior to or on index date	Record of CNS metastases prior to or on index date		edbx_get_diagnosis_solid()
Exclusion 4	Prior neoadjuvant or adjuvant treatment with a non-steroidal aromatase inhibitor (ie, anastrozole or letrozole) with disease recurrence while on or within 12 months of completing treatment.	[MBC-365; MBC-1]	Treatment with letrozole or anastrozole ≤ 12 months from MBC	Treatment with letrozole or anastrozole ≤ 12 months from MBC	Treatment with letrozole or anastrozole ≤ 12 months from MBC		
Exclusion 5	Prior treatment with any CDK4/6 inhibitor.	$[-\infty; -1]$	Prior treatment with ribociclib, palbociclib, abemaciclib	Prior treatment with ribociclib, palbociclib, abemaciclib	Prior treatment with ribociclib, palbociclib, abemaciclib		
Exclusion 6	Major surgery, chemotherapy, radiotherapy, any investigational agents, or other anti-cancer therapy within 2 weeks before randomization. Patients who received prior radiotherapy to 25% of bone marrow are not eligible independent of when it was received (see Appendix 4).	NA	NA	NA	NA		Proxied by 1st line therapy inclusion

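### Prior (neo)adjuvant endocrine therapy and chemotherapy are not among the Table 5 covariates and are controlled only through proxies, leaving possible residual confounding among recurrent patients

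*Combined protocol and SAP*

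**What the plan says.** Section 6.6.7 says that prognostic factors and auxiliary variables were chosen, and summarises them: "Such covariates comprise demographics, covariates indicating disease-severity, cancer-specific covariates as well as pathological and genetic factors". Table 5 then lists demographics, index year, ECOG, stage at initial diagnosis, de novo metastatic status, number of metastatic sites, time from initial and from metastatic diagnosis to index, histology, laboratory values and vital signs. No row records treatment given before metastatic disease, and no reason is given for leaving it out.

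Pre-metastatic drug history does enter through eligibility (Excel appendix Table 2, after section 10.4):
- Exclusion 4, window [MBC-365; MBC-1]: "Treatment with letrozole or anastrozole ≤ 12 months from MBC".
- Exclusion 5, window [-inf; -1]: "Prior treatment with ribociclib, palbociclib, abemaciclib".
- Inclusion 4, no other systemic therapy, with a window that opens only at the metastatic date.

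Excel appendix table 1 rates the prior non-steroidal aromatase inhibitor criterion as relevant and possible in all three databases. Table 7 plans an exploratory subgroup by "Disease-free interval (De-novo metastatic, ≤12 months, >12 months". No subgroup, no sensitivity analysis in Table 8 and no limitation in section 7 names prior therapy.

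**The concern.** Apart from CDK4/6 inhibitors, the eligibility rules leave in the cohort any letrozole or anastrozole stopped more than a year before metastasis, and all pre-metastatic tamoxifen, exemestane and chemotherapy. Take two recurrent patients with the same stage and the same quartile of time since diagnosis, one endocrine-naive and one with years of earlier aromatase inhibitor. As far as their history goes, they look alike to the propensity score. It is plausible that such a history affects both the decision to add palbociclib and survival. Randomisation balanced it in the trial; here nothing does so directly. A balance plot restricted to propensity-score terms cannot show imbalance in a variable outside the model.

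What is at stake is the concordance judgement. The benchmark OS hazard ratio is 0.96 (95% CI 0.78 to 1.18), and section 10.3 expects a near-null emulation with a tighter interval. The tighter the interval, the more a modest bias counts.

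**Working it through.** **1. The plan's own figures (section 10.3).** Inputs: "Assuming alpha = 0.05, 50% exposed and HR = 0.92"; "Based on a total of 1021 events in the 1:1-matched set in EDB1, we would achieve a power of 0.27"; "Based on a total of 331 events in the 1:1-matched set in EDB3, we would achieve a power of 0.11". With Schoenfeld's formula, two-sided, power = Φ(√(D/4)·|ln HR| − 1.96) and |ln 0.92| = 0.0834:
- EDB1: √(1021/4) × 0.0834 − 1.96 = 1.332 − 1.96 = −0.628, power 0.265 (stated 0.27).
- EDB3: √(331/4) × 0.0834 − 1.96 = 0.759 − 1.96 = −1.201, power 0.115 (stated 0.11).

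Both reproduce. A one-sided test would give 0.377 and 0.188 and does not.

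**2. Pooled precision.** D = 1021 + 331 = 1352. SE(log HR) = 2/√1352 = 0.0544, so the 95% interval is roughly the HR times or divided by 1.11. Power is 0.33 at HR 0.92 and 0.11 at HR 0.96.

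**3. Size of the possible bias.** The documents give neither the prevalence of prior therapy by arm after matching nor its hazard ratio for death (h). All inputs below are therefore assumptions. For an omitted binary covariate with prevalence p1 (palbociclib plus letrozole) and p0 (letrozole), the approximate factor on the HR is B = [1 + p1(h − 1)] / [1 + p0(h − 1)].
- p1 = 0.45, p0 = 0.40, h = 1.3: 1.135/1.120 = 1.013; ln B = 0.0133; 0.0133/0.0544 = 0.24 SE.
- p1 = 0.55, p0 = 0.40, h = 1.4: 1.220/1.160 = 1.052; ln B = 0.0504; 0.0504/0.0544 = 0.93 SE.

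Reversing the arms gives 1/1.013 = 0.987 and 1/1.052 = 0.951. For comparison, |ln 0.96| = 0.0408, so the two shifts are about one third of the trial's log effect (0.0133/0.0408) and somewhat more than all of it (0.0504/0.0408).

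**4. A wider range, same formula.**

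| p1 / p0 | h | B | A true 0.96 appears as | Shift in SE |
|---|---|---|---|---|
| 50% / 55% | 1.2 | 0.991 | 0.951 | −0.17 |
| 45% / 55% | 1.5 | 0.961 | 0.922 | −0.74 |
| 40% / 60% | 1.5 | 0.923 | 0.886 | −1.47 |
| 60% / 40% | 1.5 | 1.083 | 1.040 | +1.47 |

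In the third row, the chance of a nominally significant benefit at a true HR of 0.96 rises from 0.11 to 0.60. That row needs a 20-point gap after matching.

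**5. Effect of balancing de novo status.** Any imbalance is then confined to recurrent patients. If prior therapy is 60% versus 80% among them, B is 0.981 (h = 1.2) to 0.958 (h = 1.5) when half the cohort is recurrent, against 0.966 to 0.929 when all are. The proxy shrinks the bias without removing it.

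**6. What the records can support.** Exclusion 4 must draw on something beyond the line-of-therapy tables, because section 6.6.4 says those hold metastatic regimens only in EDB1 and EDB3. A source for pre-metastatic letrozole and anastrozole therefore exists. No rule reads tamoxifen, exemestane or chemotherapy before the metastatic date, so their capture is unproven.

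**The case against.** The strongest reply is that the plan already deals with most of this. De novo status, initial stage and time since diagnosis are in Table 5, and Exclusion 4 removes the most recent non-steroidal aromatase inhibitor exposure. The disease-free-interval subgroup is imputed, matched and checked for balance within stratum, and its de novo stratum should contain almost no prior (neo)adjuvant treatment. This stands: a reader might infer that prior therapy is uncontrolled, and the documents do not support that. The reply does not settle the matter for recurrent patients. The proxies do not separate treated from untreated, or endocrine therapy from chemotherapy. The de novo stratum is an exploratory subset and does not protect the primary estimate.

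Second, an exclusion needs only a positive record, whereas a covariate must also tell no treatment from treatment not recorded. Section 6.5 applies no observability criterion, section 7 names data continuity as a major challenge, and EDB1, with 1021 of 1352 events (76%), samples on metastatic diagnosis. A reader might infer that all the needed data are already in hand. That is shown only for letrozole, anastrozole and CDK4/6 inhibitors, and for letrozole and anastrozole only over one year. This also stands, and it limits the fix.

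Third, Table 5 is headed as key covariates and the balance figures could not be seen, so absence is established for Table 5 and the text only. If the variables are in the fitted model, Table 5 still needs correcting.

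**Conclusion.** The point holds as one of possible residual confounding among recurrent patients, controlled only by proxy. Adding the covariate is an inexpensive improvement; the omission does not by itself invalidate the design. That prior therapy affects both treatment choice and survival, given the listed covariates, is plausible but is not quantified anywhere in the documents. The size and direction of any bias are unknown. Under the assumed inputs of 40% versus 45% to 55% exposure and a mortality HR of 1.3 to 1.4, the factor is 1.01 to 1.05, or 0.24 to 0.93 of the pooled SE.

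A reader might infer that this bias equals the trial effect, or could create or hide it entirely. Only the upper part of an assumed range reaches the trial's 4% effect. The trial's interval of 0.78 to 1.18 and the pooled power of 0.11 at HR 0.96 also mean that neither study resolves a difference that small.

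**What to change.** - Add to Table 5, the propensity score and the imputation model a covariate for recorded aromatase inhibitor use before the metastatic date, window [-inf; MBC-1], from the drug records already read for Exclusions 4 and 5. After Exclusion 4, for letrozole and anastrozole it will in effect capture use more than a year before metastasis.
- Add recorded tamoxifen and recorded (neo)adjuvant chemotherapy in each database whose pre-metastatic records capture them, and state the reason where they do not. Section 6.6.7 already allows the covariate set to differ by database.
- Code each variable as recorded versus not recorded, with de novo patients set to none. Do not set unrecorded values to missing and impute them: every recurrent patient with an observed value would then be treated, the imputation would have no untreated recurrent donors, and missingness would depend on the value itself.
- Show these variables in the balance figures, before and after matching.
- Add a quantitative bias analysis for incomplete capture, varying the completeness of recording by arm, the residual imbalance and the mortality HR.

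The cost is a small number of derived variables, a rerun of imputation and matching, and updated counts in section 10.3. The downside is some misclassification from incomplete pre-metastatic drug history and possibly a few fewer matched pairs.
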